**Figure 4: Study Design**

Note: After the End of Study visit at 18 months of age, eligible patients will be asked to roll over into the long-term follow-up study.

ET = early termination

a All post-treatment visits will be relative to the date on which gene replacement therapy is administered, except for the 14 and 18 months of age visits, which will be relative to the patient's date of birth.

There will be at least a 4 -week dosing interval between dosing of the first 3 patients to allow review of the safety analysis from 6 time points (day 1, 2, 7, 14, 21, and 30 visits) as well as early signals of efficacy including CHOP-INTEND score prior to dosing of the next patient.

The first 3 patients enrolled must meet the criteria for the Intent-to-Treat (ITT) Population. AveXis will compare the CHOP-INTEND-1-month improvement for the AVXS-101-CL-303 patients that meet the ITT criteria to assess the clinical response to the dose  $1.1 \times 10^{14}$  vg/kg as being what was expected from the Cohort 2 patients in the Phase 1 trial (AVXS-101-CL-101). This comparison will be performed as a per patient assessment for the first 3 patients. The individual patients who receive their gene therapy at 0-3 months of age will be compared to a value of 10 CI points, while patients who receive their gene therapy at >3 but <6 months of age will be compared to a value of 5 CI points. Furthermore, patients from either age group are expected to maintain the improvement in the absence of an acute illness or perioperatively. If the expected CI improvements are observed for the first 3 ITT patients, AveXis will remove the 4-week interval between patients and proceed to dose at least 12 additional patients that meet the ITT criteria and perform safety and efficacy assessments as described elsewhere in the clinical protocol (AVXS-101-CL-303) and corresponding Statistical Analysis Plan. If the expected CI improvements are not observed for the first 3 ITT patients, AveXis will discuss next steps with the FDA before continuing study enrollment.

In an attempt to dampen the host immune response to the AAV-derived therapy, all patients will receive prophylactic prednisolone at approximately 1 mg/kg/day beginning 24 hours prior to gene replacement therapy until at least 30 days post-infusion in accordance with the specified guidelines for tapering ([Section 9.2.1](#)).

A schedule of study assessments is provided in [Appendix 5](#). Efficacy will be assessed by achievement of the key developmental milestone of functional independent sitting for at least 30 seconds at the 18 months of age study visit and survival at 14 months of age (as defined in [Section 14.1.1.1](#)). The ability to thrive and the ability to remain independent of ventilatory support (as defined in [Section 14.1.1.2](#)) will also be assessed. Additional developmental milestones will be assessed using Bayley Scales of Infant and Toddler Development© (Version 3) ([Section 11](#)). Safety will be assessed through monitoring AEs, concomitant

medication usage, physical examinations, vital sign assessments, cardiac assessments, and laboratory evaluations ([Section 12](#)). Additionally, a Data Safety Monitoring Board (DSMB) will review safety data on a quarterly basis, and will also convene within 48 hours should any patient experience an unanticipated CTCAE Grade 3, or higher AE/toxicity that is possibly, probably, or definitely related to gene replacement therapy, and is associated with clinical symptoms and/or requires medical treatment ([Section 13.1.1.1](#) and [Section 15](#)). This includes any patient death, important clinical laboratory finding, or any complication attributed to administration of gene replacement therapy. In such instances, the DSMB will review the safety information and provide its recommendation. The DSMB can recommend early termination of the study for safety reasons.

## **7.2. Number of Patients**

Up to twenty (20) patients that meet the study entry criteria will be enrolled to enable enrollment of at least 15 patients that meet ITT criteria. Study enrollment will stop as soon as practical following enrollment of the fifteenth patient that meets the ITT criteria.

## **7.3. Criteria for Study Termination**

An independent DSMB will conduct quarterly and ad hoc reviews of the emerging safety data throughout the study as described in [Section 15](#).

The study will be completed as planned but may be terminated for the following reasons:

- Development of unacceptable toxicity, defined as the occurrence of any unanticipated CTCAE Grade 3 or higher AE/toxicity that is possibly, probably, or definitely related to gene replacement therapy, and is associated with clinical symptoms and/or requires medical treatment
- DSMB can recommend early termination of the study for safety reasons
- Study is terminated by Sponsor
- Regulatory Authority recommendation

## 8. SELECTION AND WITHDRAWAL OF PATIENTS

Patients with SMA Type 1 who are < 6 months (< 180 days) of age **at the time** of gene replacement therapy (Day 1) with proven biallelic- mutations of the *SMN1* gene and 1 or 2 copies of the *SMN2* will be enrolled in this study. Patients may be of any racial, ethnic, or gender background.

### 8.1. Patient Inclusion Criteria

Patients must meet all of the following inclusion criteria:

1. Patients with SMA Type 1 as determined by the following features:
  - a. Diagnosis of SMA based on gene mutation analysis with bi-allelic *SMN1* mutations (deletion or point mutations) and 1 or 2 copies of *SMN2* (inclusive of the known *SMN2* gene modifier mutation (c.859G>C))
2. The first 3 patients enrolled must meet the criteria for the Intent-To-Treat population
3. Patients must be < 6 months (< 180 days) of age at the time of AVXS-101 infusion
4. Patients must have a swallowing evaluation test performed prior to administration of gene replacement therapy
5. Up-to-date on childhood vaccinations. Seasonal vaccinations that include palivizumab prophylaxis (also known as Synagis) to prevent respiratory syncytial virus (RSV) infections are also recommended in accordance with American Academy of Pediatrics [26]
6. Parent(s)/legal guardian(s) willing and able to complete the informed consent process and comply with study procedures and visit schedule

### 8.2. Patient Exclusion Criteria

Patients must not meet any of the following exclusion criteria:

1. Previous, planned or expected scoliosis repair surgery/procedure during the study assessment period
2. Pulse oximetry < 96% saturation at screening while the patient is awake or asleep without any supplemental oxygen or respiratory support, or for altitudes > 1000 m, oxygen saturation < 92% awake or asleep without any supplemental oxygen or respiratory support  
Pulse oximetry saturation may decrease to < 96% after screening provided that the saturation does not decrease by  $\geq 4$  percentage points
3. Tracheostomy or current use or requirement of non-invasive ventilatory support averaging  $\geq 6$  hours/day over the 7 days prior to the screening visit; or  $\geq 6$  hours/day on average during the screening period or requiring ventilatory support while awake over the 7 days prior to screening or at any point during the screening period prior to dosing

4. Patients with signs of aspiration/inability to tolerate non-thickened liquids based on a formal swallowing test performed as part of screening. Patients with a gastrostomy tube who pass the swallowing test will be allowed to enroll in the study
5. Patients whose weight-for-age is below the third percentile based on World Health Organization (WHO) Child Growth Standards [25]
6. Active viral infection (includes human immunodeficiency virus [HIV] or positive serology for hepatitis B or C, or Zika virus)
7. Serious non-respiratory tract illness requiring systemic treatment and/or hospitalization within 2 weeks prior to screening
8. Upper or lower respiratory infection requiring medical attention, medical intervention, or increase in supportive care of any manner within 4 weeks prior to screening
9. Severe non-pulmonary/respiratory tract infection (e.g., pyelonephritis or meningitis) within 4 weeks before administration of gene replacement therapy or concomitant illness that, in the opinion of the Principal Investigator, creates unnecessary risks for gene replacement therapy such as:
  - a. Major renal or hepatic impairment
  - b. Known seizure disorder
  - c. Diabetes mellitus
  - d. Idiopathic hypocalcuria
  - e. Symptomatic cardiomyopathy
10. Known allergy or hypersensitivity to prednisolone or other glucocorticosteroids or their excipients
11. Concomitant use of any of the following: drugs for the treatment of myopathy or neuropathy, agents used to treat diabetes mellitus, or ongoing immunosuppressive therapy, plasmapheresis, immunomodulators such as adalimumab, immunosuppressive therapy within 3 months prior to gene replacement therapy (e.g., corticosteroids, cyclosporine, tacrolimus, methotrexate, cyclophosphamide, IV immunoglobulin, rituximab)
12. Anti-AAV9 antibody titer > 1:50 as determined by Enzyme-linked Immunosorbent Assay (ELISA) binding immunoassay. Should a potential patient demonstrate Anti-AAV9 antibody titer > 1:50, he or she may receive retesting within 30 days of the screening period and will be eligible to participate if the Anti-AAV9 antibody titer upon retesting is ≤ 1:50
13. Clinically significant abnormal laboratory values (GGT, ALT, and AST > 3 × ULN; bilirubin ≥ 3.0 mg/dL; creatinine ≥ 1.0 mg/dL; hemoglobin < 8 or > 18 g/dL; white blood cells [WBC] > 20,000/cmm) prior to gene replacement therapy
14. Participation in recent SMA treatment clinical study (with the exception of observational Cohort studies or non-interventional studies) or receipt of an investigational or commercial compound, product or therapy administered with the intent to treat SMA (e.g., nusinersen, valproic acid) at any time prior to screening for this study. Oral β-agonists must be discontinued at least 30 days prior to gene therapy dosing. Inhaled albuterol specifically

prescribed for the purposes of respiratory (bronchodilator) management is acceptable and not a contraindication at any time prior to screening for this study

15. Expectation of major surgical procedures during the study assessment period (e.g., spinal surgery or tracheostomy)
16. Parent(s)/legal guardian(s) unable or unwilling to comply with study procedures or inability to travel for repeat visits
17. Parent(s)/legal guardian(s) unwilling to keep study results/observations confidential or to refrain from posting confidential study results/observations on social media sites
18. Parent(s)/legal guardian(s) refuses to sign consent form
19. Gestational age at birth < 35 weeks (< 245 days)

### **8.3. Patient Withdrawal Criteria**

Patients may be discontinued from the study for the following reasons:

- Death
  - An autopsy will be requested for any patient who expires following participation in a gene replacement study [25] (see Autopsy Plan in [Appendix 1](#))
- Failure to comply with protocol-required visits or study procedures for 3 or more consecutive visits that are not rescheduled, unless due to hospitalization
- Parent(s)/legal guardian(s) withdraws consent
- Investigator discretion

Early termination procedures should be completed within 14 days for any patient who prematurely discontinues the study for any reason, as indicated in [Appendix 5](#).

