All post-treatment visits will be relative to the date on which gene replacement therapy is administered, except for the 14 and 18 months of age visits, which will be relative to the patient's date of birth. For the 14 and 18 months of age visits, the patient will return within 0 to 14 days **after** the date on which the patient reaches 14 and 18 months of age, respectively. The 18 months of age visit will also serve as the End of Study visit. After the End of Study visit, eligible patients will be asked to roll over into the long-term follow-up study.

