## **10.7. Dose Adjustment Criteria**

The study investigates a 1-time IV infusion of AVXS-101; no dose adjustments are possible.

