## 11. ASSESSMENT OF EFFICACY

Efficacy will be assessed by achievement of the key developmental milestone of functional independent sitting for at least 30 seconds at the 18 months of age study visit and survival at 14 months of age (as defined in [Section 14.1.1.1](#)). The ability to thrive and the ability to remain independent of ventilatory support (as defined [Section 14.1.1.2](#)) will also be assessed at 18 months of age. Additional developmental milestones will be assessed using the Bayley Scales of Infant and Toddler Development (version 3©). Efficacy assessments will be performed at the times specified in the Table of Assessments ([Appendix 5](#)) and should be the first assessments performed at any scheduled visit. All post-treatment visits will be relative to the date on which gene replacement therapy is administered except the 14 and 18 months of age visits, which will be relative to the patient's date of birth.

Unless otherwise noted, visit windows for the outpatient follow-up visits are as follows:

- Days 7, 14, 21, and 30:  $\pm 2$  days
- Monthly visits starting at Month 2:  $\pm 7$  days
- 14 months of age visit: 0 to 14 days **after** the patient reaches 14 months of age
- 18 months of age/End of Study visit: 0 to 14 days **after** the patient reaches 18 months of age

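### Section 8.3 lets already-infused infants be discontinued after a single early-termination visit, and nothing requires their 14-month survival or 18-month sitting status to be obtained afterwards

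*Protocol*

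**What the plan says.** **Grounds for leaving.** Protocol Section 8.3 lists four reasons why a patient may be discontinued from the study: death, withdrawal of consent, and these two:
- "Failure to comply with protocol-required visits or study procedures for 3 or more consecutive visits that are not rescheduled, unless due to hospitalization"
- "Investigator discretion", with no criteria attached.

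**What is collected afterwards.** Section 8.3 continues: "Early termination procedures should be completed within 14 days for any patient who prematurely discontinues the study for any reason". Appendix 5 puts the early-termination visit in the same column as the End of Study visit. Sections 13.1.1.1 and 13.1.1.2 collect adverse events and serious adverse events up to the last study visit.

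**Treatment.** Section 10.7: "The study investigates a 1-time IV infusion of AVXS-101; no dose adjustments are possible".

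**Endpoints and analysis.** Section 14.1.1.1 sets survival free of permanent ventilation at 14 months of age and sitting for 30 seconds at the 18-month visit as co-primary endpoints. Section 11 times the first assessment: "14 months of age visit: 0 to 14 days" after that age is reached. Section 14.3.1 says that observed data are used when data are missing. Section 14.1.2.2 keeps patients who meet discontinuation criteria in the completers population but gives no outcome for them.

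**Later follow-up.** Section 7.1: "After the End of Study visit, eligible patients will be asked to roll over into the long-term follow-up study". Section 7.3 opens its list of grounds for ending the trial with: "The study will be completed as planned but may be terminated for the following reasons". Neither section says what happens to early-terminated patients, or to infused patients if the study is terminated.

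**The concern.** In a trial of repeated dosing, discontinuation usually ends exposure. Here it cannot, because the product is given once. Discontinuing an infused infant changes only what is observed.

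The outcome most easily lost is the 14-month survival endpoint. Much of it (death, tracheostomy) can be established without a clinic visit. An infant discontinued earlier need have no recorded 14-month outcome and then drops out of an analysis of observed data.

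The trial is open-label, and one ground for removal is an unrestricted investigator decision. Families who stop attending may also be those whose child is doing badly. If loss is related to outcome in this way, the remaining infants look better than the treated group as a whole. An analysis plan can decide how to score a missing outcome, but it cannot supply one that was never obtained.

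**Working it through.** **Inputs** (Protocol Sections 14.2 and 14.3.2): 15 ITT patients, about 30% excluded; sitting 30%–40% against a null of 0.1%, one-sided exact binomial, alpha 0.025; survival 80% against 25%, two-sided Fisher exact against 26 controls, alpha 0.05.

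**1. The plan's own power figures reproduce.** Fifteen less 30% leaves 10 or 11.
- Sitting: the chance of at least one sitter under the null is 1 − 0.999^10 = 0.0100 or 1 − 0.999^11 = 0.0109, both below 0.025, so one sitter rejects. Power is 1 − 0.7^10 = 97.2% to 1 − 0.6^11 = 99.6%, against a stated figure above 90%.
- Survival: enumerating all Fisher tables with random controls gives 81.9% (n = 10) and 85.9% (n = 11), against a stated figure above 80%.

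The 30% allowance therefore covers lost precision. It does not address loss that depends on outcome.

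**2. Illustration for survival (assumed data).** Suppose 15 ITT infants. Three are discontinued before 14 months and all three later die or need permanent ventilation; of the other 12, nine survive. A 25% rate in 26 controls is 6.5 patients, so both neighbours are shown (6/26 = 23.1%, 7/26 = 26.9%).

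With x survivors of n treated, c survivors of 26 controls and s = x + c, each table has probability C(n,x)·C(26,s−x)/C(n+26,s). The two-sided p sums the tables no more probable than the one observed.

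| Treated survivors | vs 6/26 | vs 7/26 |
|---|---|---|
| 9/12 = 75% (observed only) | 0.004 | 0.012 |
| 9/15 = 60% (all followed) | 0.041 | 0.051 |
| 10/15 = 67% | 0.009 | 0.021 |
| 12/15 = 80% (planned rate) | 0.001 | 0.001 |

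The decision at 0.05 changes only for 9/15 against 7/26.

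**3. Survival power when k of 15 have no outcome.** The others survive at 80% and controls are random at 25%. The last column is a worst case, with every lost infant a failure.

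| k | Observed data | Lost infants all failures |
|---|---|---|
| 2 | 90.3% | 78.0% |
| 4 | 85.9% | 50.9% |
| 5 | 81.9% | 34.7% |

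The gap is what an observed-data analysis would hide if every lost infant had failed. With k = 4, true survival is 0.8 × 11/15 = 59%, well below the plan's assumption.

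**4. Sitting.** One sitter rejects whether n is 12 (1 − 0.999^12 = 0.012) or 15 (1 − 0.999^15 = 0.015). The estimate does move: at the 40% assumption, 0.40 × 15 = 6 sitters; if the three lost infants are non-sitters, 6/12 = 50% is reported instead of 6/15 = 40%.

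**5. Search for a collection rule.** Sections 7.1, 7.3, 8.3, 11, 12, 13, 14 and Appendix 5 contain no requirement to obtain 14- or 18-month status after an early-termination visit.

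**The case against.** The case against has substance.

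- **The grounds are narrower than they look.** Section 8.3 is permissive, counts only visits that were not rescheduled, and exempts hospitalization. Section 7.1 and Appendix 5 call for missed visits to be rescheduled within 7 days. Hospitalized infants, an obvious route to informative loss, are thus not removed under the visit rule. This stands and makes the problem rarer. It does not touch investigator discretion.
- **The early-termination visit is substantial.** Appendix 5 gives it the End of Study assessments, including Bayley, chemistry, CK-MB, ECG, Holter and echocardiogram. That is true, but before 14 months it cannot supply a 14-month outcome.
- **Remote data are weaker.** Under Section 12.1.7, ventilation hours are read from a device card by study staff at visits, and the endpoint also excludes acute reversible illness. A telephone report is less precise. This limits the remedy but does not argue for collecting nothing.
- **The illustration is unfavourable by choice.** It implies 60% true survival. The protocol expects at least 80%, and Section 5.4 reports no deaths or permanent ventilation among 12 Cohort 2 patients.

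A reader might infer more: that these outcomes and long-term safety are never collected, that early-terminated infants are barred from long-term follow-up, or that a toxicity termination would end safety follow-up of infused infants. The document does not support this. Section 13.4 still asks for related serious events discovered after the study, and Section 8.3 and Appendix 1 request an autopsy after any death. An infant leaving between 14 and 18 months already has the survival outcome. On long-term follow-up and on data collection after termination the protocol is silent, and silence is not a bar. Nor is there a case for abolishing investigator discretion or rewriting the termination criteria, which would go further than the gap requires.

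**Conclusion.** The point holds as a gap in the data-collection rule: an infused infant can leave on two non-consent grounds, and later collection of a co-primary outcome is permitted by silence but not required. It matters mainly for 14-month survival. Each of 15 patients is 6.7% of the primary population, and three lost failures raise observed survival from 60% to 75% in the illustration. Significance is lost on full follow-up only against 7/26 controls. At the planned 80% survival, the result is secure either way. For sitting, the risk is an inflated estimate, not a false rejection.

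The size rests on assumptions that the document cannot confirm: how many infants are discontinued before 14 months, and that their later outcomes are poor. The direction of bias follows from the second; if loss is unrelated to outcome, only precision suffers. The stated power figures are not in error.

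**What to change.** In Section 8.3, separate stopping study visits from stopping data collection. Unless consent to further data collection is withdrawn, obtain for every infused patient:
- vital status, tracheostomy and ventilation status at 14 and 18 months of age, by telephone, medical records, or device data where available;
- sitting at 18 months, by visit or family video where possible (Sections 11.1 and 11.3 already use family video).

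Record the source of each ventilation report, so that remote reports can be told apart from device data.

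As clarifications, state in Section 7.1 whether early-terminated patients may enter the long-term follow-up study, and in Section 7.3 what data collection continues for infused patients if the study is terminated.

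The cost is protocol and consent wording plus one or two contacts per non-attending patient. The drawback is that ventilation hours reported remotely are less precise than device-card data.

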## 9. TREATMENT OF PATIENTS

It is the responsibility of the Investigator to ensure the safe storage and administration of gene replacement therapy.

### 9.1. Description of Product

The biological product is a non-replicating recombinant AAV9 containing the complimentary deoxyribonucleic acid (cDNA) of the human SMN gene under the control of the cytomegalovirus (CMV) enhancer/chicken- $\beta$ -actin-hybrid promoter (CB). The AAV inverted terminal repeat (ITR) has been modified to promote intramolecular annealing of the transgene, thus forming a double-stranded transgene ready for transcription. This modified ITR, termed a “self-complementary” (sc) ITR, has been shown to significantly increase the speed of which the transgene is transcribed, and the resulting protein is produced. The biological product, called AVXS-101 (formerly scAAV9.CB.hSMN), expresses the human SMN protein in transduced cells.

**Table 5: Investigational Product**

	Investigational Product
Product Name:	AVXS-101
Dosage Form:	Equivalent to the dose received by the second dosing Cohort in the Phase 1 study
Unit Dose	$1.1 \times 10^{14}$ vg/kg; Equivalent to the dose received by the Cohort 2 in the Phase 1 study (AVXS-101-CL-101) as determined by direct product testing with improved analytical methods.
Route of Administration	Intravenous infusion
Physical Description	AVXS-101 is a clear, colorless liquid.

